### 3.2.1 Screen Failure

A screen failure is defined as a subject who has signed the ICF, does not meet all the entry criteria outlined in Section 4 of this protocol (note that this includes assessments through Visit 1), and was not randomized to receive study treatment. The Investigator is responsible for keeping a record of all subjects screened for entry into the study and subsequently excluded. The reason(s) for exclusion will be recorded in the source documents and on the Screening log. Screen failure subjects will have only their consent, demographic and reason for screen failure (including, where applicable, the unmet inclusion or exclusion criteria) data entered into the electronic data capture (EDC) system, unless an adverse event was responsible for the subject's screen failure, in which case all data collected for that subject during the screening process will be entered into the EDC system.

### 3.3 Visit 2 (Day -10 ± 2 days)

Subjects will report to the CRU in the morning. The following procedures will be performed:

- Review of medical history;
- Review of medications and supplements;
- Review inclusion and exclusion criteria;
- Measurement of vital signs (weight, seated SBP/DBP, and heart rate);
- Subjects will be fitted with the CGM device and data recording will begin;
- Dispensing of Run-in Placebo capsules
- Dispensing of diaries;
- Subjects will be reminded to fast for a minimum of 10 hours prior to arrival on Visit 3 (Day 1 ± 2 days).

### **3.4 Visit 3 (Day 1 ± 2 days)**

Subjects will report to the CRU in the morning in fasting state. The following procedures will be performed:

- Collect data from CGM monitor;
- Review of medications and supplements;
- Collect and review diary;
- Measurement of vital signs (weight, seated SBP/DBP, and heart rate);
- Urine pregnancy Test for women of childbearing potential
- Collect fasting blood samples for serum chemistry (with fasting plasma glucose/FPG) and HbA1c;
- Review inclusion and exclusion criteria.
- Randomization of subjects to their individual study treatment sequence;
- Dispensing of IMP and instructions on use of IMP.
- Adverse events will be monitored and recorded.

### **3.5 Visit 4 (Day 18 ± 2 days)**

Subjects will report to the CRU in the morning. The following procedures will be performed:

- Adverse events will be monitored and recorded;
- Review of medications and supplements;
- Measurement of vital signs (weight, seated SBP/DBP, and heart rate);
- Subjects will be fitted with the CGM device and data recording will begin;

- Dispensing of diaries;
- Re-dispensing of IMP;
- Assessment of compliance to IMP;
- Subjects will be reminded to fast for a minimum of 10 hours prior to arrival on Visit 5 (Day 28 ± 2 days).

### **3.6 Visit 5 (Day 28 ± 2 days)**

Subjects will report to the CRU in the morning in fasting condition. The following procedures will be performed:

- Collect data from CGM monitor;
- Review of medications and supplements;
- Collect and review diary;
- Measurement of vital signs (weight, seated SBP/DBP, and heart rate);
- Urine pregnancy Test for women of childbearing potential
- Collect fasting blood samples for serum chemistry (with fasting plasma glucose/FPG) and HbA1c;
- Assessment of compliance to IMP;
- Crossover of study treatment;
- Dispensing of IMP;
- Adverse events will be monitored and recorded.

### **3.7 Visit 6 (Day 46 ± 2 days)**

Subjects will report to the CRU in the morning. The following procedures will be performed:

- Review of medications and supplements;
- Adverse events will be monitored and recorded;
- Measurement of vital signs (weight, seated SBP/DBP, and heart rate);
- Subjects will be fitted with the CGM device and data recording will begin;
- Dispensing of diaries;
- Re-dispensing of IMP;
- Assessment of compliance with IMP;
- Subjects will be reminded to fast for a minimum of 10 hours prior to arrival on Visit 7

(Day 56 ± 2 days)

### 3.8 Visit 7 (Day 56 ± 2 days)

Subjects will report to the CRU in the morning in fasting condition. The following procedures will be performed:

- Review of medications and supplements;
- Collect data from CGM monitor;
- Collect and review diary;
- Measurement of vital signs (weight, seated SBP/DBP, and heart rate);
- Physical examination;
- Collect fasting blood samples for hematology, serum chemistry (with fasting plasma glucose/FPG), HbA1c and urinalysis;
- Returning of IMP;
- Assessment of compliance to IMP;
- Adverse events will be monitored and recorded.
- Discharge from the study.

Any subject with a possible study treatment related AE at Visit 7 will be followed until resolution or stabilization of the event. Further, any SAE, whether or not related to study treatment that occurs within 14 days following the last dose of study treatment will be followed until resolution or stabilization of the event. This may require additional clinical assessments and laboratory tests. The follow-up results will be recorded in the subject's source documentation and in the electronic case report form (eCRF).

### 3.9 Early Withdrawal (EW)

If a randomized subject is withdrawn from the study prior to completing study treatment, the subject will be discharged from the study after following procedures will be performed:

- Review of medications and supplements;
- Vital signs (including weight, seated SBP/DBP, and heart rate);
- Physical examination;
- Collect data from CGM monitor (if applicable);
- Collect and review diary (if applicable);
- Collection of fasted blood and urine samples for:

- Clinical safety labs, including hematology, serum chemistry (with fasting plasma glucose/FPG), HbA1c and urinalysis (see Section 6.3.5 for list of tests).
- Returning of IMP;
- Assessment of compliance to IMP;
- Adverse events will be monitored and recorded;
- Discharge from the study.

Any subject with a possible study treatment related AE at the time of EW will be followed until resolution or stabilization of the event.

### **3.10 Schedule of Events**

Table 1 below describes the daily schedule of events from Screening Visit 1 through Visit 7.

**Table 1. Daily Schedule of Events from Screening Through Visit 7**

Visit	Screening Visit 1	Visit 2	Randomization Visit 3	Visit 4	Visit 5	Visit 6	Visit 7	EW
Study Day	-21	-10	1	18	28	46	56	
Window days	$\pm 2$	$\pm 2$	$\pm 2$	$\pm 2$	$\pm 2$	$\pm 2$	$\pm 2$	
Informed Consent	X							
Medical History	X	X						
Demographics	X							
Concomitant Medications	X	X	X	X	X	X	X	X
Inclusion/Exclusion Criteria	X	X	X					
Physical Exam	X						X	X
ECG	X							
Vital Signs	X	X	X	X	X	X	X	X
Serum Pregnancy Test	X							
Urine Pregnancy Test			X		X			
Infectious Serology (HIV, HBV, HCV)	X							
C-peptide, TSH, FSH	X							
Hematology	X						X	X
Serum Chemistry (with FPG)	X		X		X		X	X
HbA1c	X		X		X		X	X
Urinalysis	X						X	X
Randomization			X					
Treatment Crossover					X			
Treatment Compliance			X	X	X	X	X	X
Treatment dispensing/returning		X	X	X	X	X	X	X
CGM Monitoring		X	X	X	X	X	X	X
Diary dispensing/collecting		X	X	X	X	X	X	X
Adverse Events			X	X	X	X	X	X
Study Disposition							X	X

**Table 1 Footnotes**

Vital signs include height, weight, heart rate, SBP, and DBP. Height will be measured at Screening only, without shoes.

CGM monitor applied at Visits 2, 4, and 6; removed and downloaded at visits 3, 5, and 7 (or EW if applicable).

Diary dispensed at Visits 2, 4, and 6; collected and reviewed at visits 3, 5, and 7 (or EW if applicable).

## 4 STUDY SUBJECT SELECTION

### 4.1 Inclusion Criteria

Each subject must meet all of the following criteria to be eligible for study participation:

1. Male and female (non-childbearing potential) subjects aged 18 and older.
2. Body mass index (BMI) of 19-30 kg/m^2 at Screening and stable weight, with no more than 5 kg gain or loss in the 3 months prior to Screening.
3. T1D subjects must have:
  - a. A documented history of type 1 diabetes for at least 6 months
  - b. Should be on an MDI regimen
  - c. C peptide levels of < 0.7 ng/mL
  - d. HbA1C  $\geq$  6.5% to  $\leq$  10%
4. Females of childbearing potential must have a negative serum pregnancy test result at Screening.
5. Females who are not of childbearing potential are defined as:
  - a. post-menopausal (defined as at least 12 months with no menses in women  $\geq$  45 years of age) or
  - b. has had a hysterectomy and/or bilateral oophorectomy, or had bilateral tubal ligation or occlusion at least 6 weeks prior to Screening
6. Subjects who are of childbearing potential must:
  - a. agree to remain abstinent from heterosexual activity† or agree to use (or have their partner use) acceptable contraception to prevent pregnancy within the projected duration of the trial and for 14 days after the last dose of blinded investigational product. Two methods of contraception will be used to avoid pregnancy. Acceptable combinations of methods include:
    - i. Use of one of the following double-barrier methods: diaphragm with spermicide and a condom; cervical cap and a condom; or a contraceptive sponge and condom
    - ii. Use of hormonal contraception (any registered and marketed contraceptive agent that contains an estrogen and/or a progestational agent [including oral, subcutaneous, intrauterine and intramuscular agents, and cutaneous patch]) with one of the following: diaphragm with spermicide; cervical cap; contraceptive sponge; condom; vasectomy; or IUD.
    - iii. Use of an IUD with one of the following: condom; diaphragm with spermicide; contraceptive sponge; vasectomy; or hormonal contraception (see above).
    - iv. Vasectomy with one of the following: diaphragm with spermicide; cervical cap; contraceptive sponge; condom; IUD; or hormonal contraception (see above).

†Abstinence can be used as the sole method of contraception if it is in line with the subject's preferred and usual lifestyle and if considered acceptable by local regulatory agencies and ethics committees. Periodic abstinence (e.g., calendar, ovulation, sympto-thermal, post-ovulation methods, etc.) and withdrawal are not acceptable methods of contraception.

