	
6. Other measures of hypoglycemia over the last 10 days of each treatment period:
 

a. Severe hypoglycemia (SH) events (impaired or loss of consciousness requiring assistance of another)

b. Documented symptomatic hypoglycemia (an event during which typical symptoms of hypoglycemia are accompanied by a measured plasma glucose concentration <70 mg/dl (3.9 mmol/L))

c. Total time <70 mg/dL by CGM

d. Nocturnal hypoglycemia, severe or documented symptomatic episodes (as defined above) occurring after the subject has retired for the primary sleeping period

 
Safety assessments evaluating:
 

• Changes in clinical laboratory tests (hematology, chemistry, urinalysis);

• Collection of adverse events (AEs);

• Changes in Vital sign measurements

Duration of Participation	Including screening period, subjects will participate in this study for about 77 days (11 weeks).
Subject Selection Criteria	
Inclusion Criteria
 
Each subject must meet all of the following criteria to be eligible for study participation:
 

1. Male and female subjects aged 18 and older.

2. Body mass index (BMI) of 19-30 kg/m^2 at Screening and stable weight, with no more than 5 kg gain or loss in the 3 months prior to Screening.

3. T1D subjects must have:

a. A documented history of type 1 diabetes for at least 6 months

b. Should be on an MDI regimen

c. C peptide levels of < 0.7 ng/mL

d. HbA1C ≥ 6.5% to ≤10%

4. Females of childbearing potential must have a negative serum pregnancy test result at Screening.

5. Females who are not of childbearing potential are defined as:

a. post-menopausal (defined as at least 12 months with no menses in women ≥45 years of age) or

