### **3.2 Screening (-21 Days prior to Randomization)**

At the Screening Visit, potential subjects will be given a detailed oral presentation describing the nature, purpose, risks, and requirements of the study and will receive detailed written information. Subjects will be given ample time to consider participation and ask questions which will be adequately addressed by site personnel.

Once the subject is satisfied that he/she is willing to participate in the study, he/she will be asked to sign the study ICF (refer to Section 11.2.4 for further details regarding the ICF). The investigational site personnel obtaining written consent from the subject will also sign the consent form.

Once signed, the Investigator will retain the original ICF for the subject's study records and provide the subject with a signed copy. The investigator will verify that informed consent has been obtained from each subject prior to enrollment into the study and prior to the subject undergoing any study-related procedures.

Screening activities after obtaining informed consent will be conducted and consist of the following:

- Completion of medical history (including start date for T1DM),
- Collection of demographic data (sex, age, race/ethnicity);

- Review of prior and current medications and supplements;
- Review inclusion and exclusion criteria.
- Physical examination.
- Measurement of height and weight.
- Measurement of vital signs (SBP/DBP and heart rate).
- 12-lead electrocardiogram (ECG).
- Collection of fasted blood and urine samples for:
  - Clinical safety labs, including hematology, serum chemistry (with fasting plasma glucose/FPG, HbA1c, C-peptide, and serum thyrotropin/TSH, FSH to confirm postmenopausal status in women, and urinalysis (see Section 6.3.5 for list of tests);
  - Infectious serology (HIV, HBV, HCV);
  - Serum pregnancy Test for women of childbearing potential

For subjects who meet eligibility criteria based on the Screening assessments, instruction will be provided on the following:

- Use of adequate contraceptive methods (see Section 4.1) for the duration of the study (Screening through Visit 7);
- Minimal use of concomitant medications during the study, if possible, and avoid prohibited medications as defined in Section 5.7;
- Maintenance of usual dietary habits and avoidance of drastic changes, such as a conversion to a vegetarian diet;

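### Section 4.1 item 1 bars women of childbearing potential whom the Synopsis and other criteria admit; if they are eligible, the 7.4.2 pregnancy procedure omits the exposed subject

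*Protocol*

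**What the plan says.** Section 4.1 of the protocol opens with "Each subject must meet all of the following criteria to be eligible for study participation". Item 1 of that list is "Male and female (non-childbearing potential) subjects aged 18 and older". In the Synopsis, item 1 is "Male and female subjects aged 18 and older", with no parenthetical.

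Item 4, in both places, is "Females of childbearing potential must have a negative serum pregnancy test result at Screening". Item 6 begins "Subjects who are of childbearing potential must" and sets out contraception rules that run to 14 days after the last dose. Item 5 defines non-childbearing potential: post-menopausal at age 45 or over, or surgically sterile.

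Section 3.2 lists a "Serum pregnancy Test for women of childbearing potential". Sections 3.4 (Visit 3, randomization) and 3.6 (Visit 5, crossover) each list a "Urine pregnancy Test for women of childbearing potential". Table 1 carries the same tests as rows.

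Section 4.3 makes pregnancy of a subject a reason to end participation, and exclusion 17 bars pregnant or breast-feeding subjects. Section 7.4.2 contains the only dedicated pregnancy procedure: a report within 24 hours, an Exposure In Utero form, follow-up to the end of the pregnancy and a record of the outcome. Both its trigger and its follow-up duty name the partner of a subject. Section 7.5.1 says that animal reproductive studies have not been done and that the risk to a fetus is unknown.

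**The concern.** An inclusion list that must be met in full cannot both exclude a class of women and set conditions for their entry. A site that follows item 1 would turn away every woman of childbearing potential; by item 5, it could enrol a woman under 45 only if she were surgically sterile. A site that follows the Synopsis would enrol women of childbearing potential and breach Section 4.1 each time, and Section 12.1 has the monitor record subjects enrolled without meeting all criteria as deviations. With three sites, the population could differ from site to site for no reason other than drafting.

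The second issue depends on how the first is settled. If these women enrol, the protocol follows a pregnancy in a partner to its outcome, but sets no matching duty for a pregnancy in a woman who took the drug herself. Since fetal risk is unknown, hers is the outcome the sponsor most needs.

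**Working it through.** The documents give no figure on eligibility, so the first step is a comparison of texts.

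**Step 1. Which provisions conflict with item 1, and which can stand beside it?**

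| Provision | If item 1 governs | Reading |
|---|---|---|
| Synopsis item 1 | States a wider population | Direct conflict |
| Item 4 (4.1 and Synopsis) | Sets an entry condition for women who cannot enter | Direct conflict |
| Item 6 (4.1 and Synopsis) | Its female provisions apply to no one; wording on subjects and their partners could still serve men | Conflict in part |
| Urine test at Visit 3 (3.4) | Tests, at randomization, women who should already have been screened out | Conflict |
| Urine test at Visit 5 (3.6) | Tests women of childbearing potential after about four weeks of dosing | Clearest procedural conflict |
| "Serum Pregnancy Test" at Screening (3.2, Table 1) | Can serve as a check before eligibility is settled | Supporting evidence only |
| Pregnancy as a reason to end participation (4.3) | Can stand as a precaution | Supporting evidence only |
| Partner-only procedure (7.4.2) | Coherent | Agrees with item 1 |

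The Visit 5 test matters most among the procedures: it falls on treatment, after all eligibility checks, and is confined to women whom item 1 would have kept out.

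**Step 2. If these women enrol, do the general safety routes replace the 7.4.2 procedure?**

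- Section 7.3: pregnancy is not a listed serious outcome. Congenital anomaly is, but it would have to fall inside the reporting window.
- Section 7.4.2: SAEs must be reported up to 30 days after the last dose.
- Section 7.8: SAEs inside that window are followed to resolution or stabilization.
- Section 7.9: follow-up of a significant finding may stop once it stabilizes or is explained as unrelated.
- Section 4.3: the investigator consults the sponsor and Medical Monitor before removing a subject; nothing is said about the outcome of the pregnancy.

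**Step 3. Does the SAE window reach a term birth?**

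Inputs: last dose near Visit 7, Day 56 (Table 1); window 30 days (7.4.2). Assumption, not in the documents: about 38 weeks from conception to delivery.

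- End of window: 56 + 30 = Day 86. With the 2-day visit allowance, 58 + 30 = Day 88.
- Conception on Day 1: term is near Day 1 + 38 × 7 = 1 + 266 = Day 267, which is 267 − 86 = 181 days after the window closes.
- Time covered for that pregnancy: 86 − 1 = 85 days, or 85 / 7 = 12.1 weeks.
- Extreme case, conception dated from Screening (Day −21): 86 + 21 = 107 days, or 107 / 7 = 15.3 weeks.

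Even the extreme case covers less than half of 38 weeks, so the result does not turn on the exact gestation assumed. For a woman withdrawn because she is pregnant, dosing stops sooner and the window closes sooner. A congenital anomaly first seen at a term birth would fall outside mandatory reporting.

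**The case against.** The best reply is that intent cannot be read off the page. The partner-only wording in 7.4.2 agrees with item 1, and with no animal reproductive data, exclusion would be the more cautious design. That stands: the documents favour eligibility but do not settle it, so the sponsor has to be asked.

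Three stronger readings are tempting and are not supported.

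- A reader might count every mention of pregnancy or childbearing status and treat the total as proof that item 1 is the slip. The mentions are not independent. Synopsis items 4 and 6 repeat 4.1, and the Table 1 rows repeat the visit text. The SAP's planned listing of childbearing status fits either reading.
- A reader might say that the Screening test and the 4.3 rule contradict item 1. Both can stand as safeguards under an exclusion, particularly as item 5 counts tubal ligation as non-childbearing and exclusion 17 bars pregnant subjects in any case.
- A reader might infer that Section 3.2, which asks for contraception through Visit 7, overrides the further 14 days in item 6. Section 3.2 refers to Section 4.1 for the rule, so this is at most a point of tidiness.

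It is also fair to say that a literal item 1 errs toward exclusion rather than harm, and that general reporting gives partial cover. This limits the size of the problem but removes neither the contradiction nor the conditional gap.

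**Conclusion.** The eligibility contradiction is established on the text. Item 1 of Section 4.1 conflicts with Synopsis item 1, with item 4, with the female provisions of item 6, and with the urine tests at Visits 3 and 5.

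The reporting gap is conditional. If women of childbearing potential are excluded, 7.4.2 is consistent as it stands, and it should not be called an error in its own right. If they are eligible, as most of the text indicates, 7.4.2 omits the directly exposed subject, and the general SAE window closes about 181 days before a term birth conceived on Day 1, assuming 38 weeks.

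The matter is worth correcting but modest: about 26 subjects and few if any pregnancies expected. No estimate, test or sample size is affected.

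**What to change.** The sponsor should first confirm which population is intended.

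**If women of childbearing potential are eligible:** delete the parenthetical from item 1 of Section 4.1, so that it matches the Synopsis. In 7.4.2, insert *a subject or* ahead of the mention of the partner in the trigger sentence, and make the follow-up duty apply to *the pregnant subject or partner*. The 24-hour report, the Exposure In Utero form and follow-up to outcome then cover both. The sponsor should note that Table 1 has no pregnancy test after Visit 5, so a pregnancy arising in the second treatment period would come to light only by self-report.

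**If exclusion is intended:** restrict Synopsis item 1 to match 4.1, and remove item 4 and the female provisions of item 6 in both places. The urine tests at Visits 3 and 5 would need to be dropped or reworded, since the women they name would not be enrolled. Keep the Screening pregnancy test, exclusion 17 and the 4.3 pregnancy rule: they cost almost nothing and still protect against a misclassified subject. The partner wording in 7.4.2 can stay.

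The cost either way is a short protocol amendment with IRB approval before it takes effect (Section 10). Sample size and analysis do not change.

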## 4.2 Exclusion Criteria

Subjects who meet any of the following criteria must be excluded from the study:

1. Clinical diagnosis of type 2 diabetes;
2. Evidence of unawareness of hypoglycemia unawareness, a documented plasma glucose  $\leq 50$  mg/dL in the absence of symptoms of hypoglycemia at Screening.
3. FPG  $>300$  mg/dL at Screening; a single repeat test is allowable.
4. Use of the following medications:
  - a. Administration of thyroid preparations or thyroxine (except in subjects on stable replacement therapy) within 6 weeks prior to Screening.
  - b. Administration of systemic long-acting corticosteroids within two months or prolonged use (more than one week) of other systemic corticosteroids or inhaled corticosteroids (if daily dosage is  $> 1,000$   $\mu$ g equivalent beclomethasone) within 30 days prior to Screening. Intra-articular and/or topical corticosteroids are not considered systemic.
5. Laboratory abnormalities at Screening including:
  - a. Abnormal serum thyrotropin (TSH) levels below the lower limit of normal or  $>1.5X$  the upper limit of normal
  - b. Elevated liver enzymes (alanine transaminase (ALT), alanine aminotransferase (AST), alkaline phosphatase)  $>2X$  the upper limit of normal.
  - c. Very high triglyceride levels ( $>600$  mg/dL); a single repeat test is allowable.
  - d. Any relevant abnormality that would interfere with the efficacy or the safety assessments during study treatment administration.
6. Subject has a Screening systolic blood pressure  $\geq 165$  mmHg or diastolic blood pressure  $\geq 100$  mmHg. Subjects will be allowed to take a BP rescue medication.
7. Any clinically significant ECG abnormality at Screening or cardiovascular disease. Clinically significant cardiovascular disease will include:
  - a. History of stroke, transient ischemic attack, or myocardial infarction within 6 months prior to Screening,
8. History of or currently have New York Heart Associate Class II-IV heart failure prior to Screening.

9. Presence of any clinically significant endocrine disease according to the Investigator (euthyroid subjects on replacement therapy will be included if the dosage of thyroxine is stable for at least six weeks prior to Screening).
10. Presence of any clinically significant condition (in the opinion of the Investigator) that might interfere with the evaluation of study medication, such as significant renal, hepatic, gastrointestinal (GI), cardiovascular (CV), immune disease, blood dyscrasias or any disorders causing hemolysis or unstable red blood cells, or clinically important hematological disorders (i.e. aplastic anemia, myeloproliferative or myelodysplastic syndromes, thrombocytopenia) at Screening.
11. History of gastrointestinal disorders (e.g. hypochlorhydria) with the potential to interfere with drug absorption.
12. Presence or history of cancer within the past 5 years of Screening, with the exception of adequately-treated localized basal cell skin cancer or in situ uterine cervical cancer.
  - a. A subject with a history of malignancy >5 years prior to Screening should have no evidence of residual or recurrent disease.
  - b. A subject with a history of melanoma, leukemia, lymphoma, or renal carcinoma is excluded.
13. Positive history of active liver disease (other than non-alcoholic hepatic steatosis), including chronic hepatitis B or C, primary biliary cirrhosis, or active symptomatic gallbladder disease.
14. Positive history of HIV.
15. Known allergy to soy.
16. Subject is on a weight loss program and is not in the maintenance phase, or subject has started weight loss medication (e.g., orlistat or liraglutide), within 8 weeks prior to Screening. Subjects who have had bariatric surgery are also excluded.
17. Subject is pregnant or breast-feeding.
18. Subject is a user of recreational or illicit drugs or has had a recent history (within 1 year of Screening) of drug or alcohol abuse or dependence. (Note: Alcohol abuse includes heavy alcohol intake as defined by >3 drinks per day or >14 drinks per week, or binge drinking) at Screening.
19. At the Principal Investigator's discretion, any condition or other factor that is deemed unsuitable for subject enrollment into the study.

